### 8.3 Statistical methods

Describe the statistical methods (or non-statistical methods of analysis) that will be employed.

The normality of the data will be tested before performing analyses, and transformations will be made if needed. Mixed effect models will be used to determine between-group changes over time and between group differences in mean values following the treatments. Treatment will be included as a fixed effect. Subject will be included as a random effect.

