## 1.0 Objectives

### 1.1 Study Objectives

Describe the purpose, specific aims or objectives. State the hypotheses to be tested.

The purpose of the study is to evaluate the effects of nighttime peanut consumption (i.e., after dinner and before sleep) on fasting blood glucose levels, longer-term blood glucose control, and risk factors for cardiovascular disease. Furthermore, this study will investigate the relationship between the microbiota, shifts in the microbiota with peanut consumption and the effect on blood glucose regulation. There is some emerging evidence that the microbiome predicts glycemic response and this study would provide the first robust test of the role of the microbiome in blood glucose regulation in response to peanut consumption.

The aims of the study are as follows:

- To determine the effect of consuming one ounce of peanuts as an evening snack (after dinner and before sleep) on glycemic control and risk factors for cardiovascular disease, compared with an isocaloric high carbohydrate snack, in people with impaired fasting glucose.
- To assess changes in the profile of the gut bacterial community in response to the peanut treatment, compared with an isocaloric high carbohydrate snack, in people with impaired fasting glucose.
- To investigate the relationship between markers of glycemic control, after each treatment, and shifts in the microbiota to elucidate the role of the microbiome in glucose regulation.

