#### Hypothesis

- consuming peanuts as an evening snack will reduce fasting glucose levels compared to an isocaloric high carbohydrate control snack.
- Improvements in fasting glucose levels with peanut consumption will be correlated with favorable shifts in the microbiota i.e. peanut consumption will result in enrichment of bacteria known to be biomarkers of a healthy gut and these shifts will be associated with the magnitude of blood glucose lowering observed.

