These observations may be explained in part by a blunting of the Dawn Phenomenon. The Dawn Phenomenon is characterized by a rise in early morning fasting blood glucose. At present it is thought that the Dawn Phenomenon is caused by excessive glucose production by the liver “at dawn”, in the absence of insulin, and thus elevations in fasting blood glucose are observed. Identifying successful strategies to counteract this physiological effect is of importance because a rise in fasting blood glucose levels of more than 50 mg/dL can result in daylong hyperglycemia. Furthermore, the Dawn Phenomenon is not effectively treated by the current oral hypoglycemic agents and therefore an opportunity exists to identify an effective strategy to blunt the Dawn Phenomenon, a substantial cause of poor glycemic control, and improve overall glycemic control.

Emerging evidence suggests that the microbiome may determine glycemic response. Large individual variation has been observed in glycemic response to foods differing in glycemic index, and this has largely been poorly understood. However, recently, a one-week randomized controlled trial of two different bread treatments showed that the glycemic response to the bread type could be predicted based on the microbiome. This paper, published in Cell Metabolism (impact factor 18.16), provides some of the first evidence that the microbiome may mediate glycemic response. Although this study was only one week long so changes in the microbiome could not be detected. Therefore, we propose to conduct a 6 week study to allow investigation of: 1) the effect of the microbiome on glycemic response to peanuts vs. the control snack; and 2) how changes in the microbiome in response to peanut consumption correlate with changes in glucose regulation.

Recent data suggests that tree nut consumption for between three and six weeks changes the microbiome; no studies have assessed the effect of peanuts on the microbiome. In many of these studies there were changes in the relative abundance of microbiota known to be associated with beneficial health effects.

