## 7.0 Study Design and Procedures

### 7.1 Study Design

Describe and explain the study design.

A two-period randomized crossover trial will be conducted. Participants will be randomized to receive each treatment for 6 weeks followed by a minimum 4-week wash-out period. During the peanut treatment, participants will consume one ounce per day (28 g) of peanuts as an evening snack. The control treatments will be an isocaloric high carbohydrate snack (crackers + spread) consumed after the evening meal. The peanuts and control foods will be provided to the participants every two weeks during the treatment periods; these foods will be purchased from one of the local supermarkets. Participants will be given instructions about when to consume the foods.

Fasting blood glucose, fructosamine, insulin, weight, lipids and lipoproteins, central and peripheral blood pressure and arterial stiffness will be measured at the beginning and the end of each treatment period. Fecal samples will be provided at the beginning and the end of each treatment period for assessment of the microbiome. A 24-hour dietary recall will be completed at the beginning and end of each diet to determine how consuming the evening snack influences overall dietary intake (including calorie and macronutrient intake and overall diet quality).

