### 7.2.2 EXAMPLE: Visit 2 or Day 2 or Post-test, etc. (format accordingly)

Provide a description as defined above and format accordingly.

Baseline and endpoint visits (8 total):

At the beginning and end of each diet period, two fasting blood samples will be collected (separated by at least 24 hours) for analysis of biochemical endpoints. Body weight will be taken

and vascular health assessments using the SphygmoCor will be performed at the beginning and end of each diet period. Participants will also complete a fecal collection at the beginning and end of each treatment period. Participants will complete a 24-hour dietary recall at the beginning and end of each treatment period.

**Plasma/serum analysis:** In addition to the blood taken at screening, 12 hour fasting blood samples also will be taken on two consecutive days at the beginning and end of each treatment period for a total of 8 times. Approximately 60 ml (about 4 Tbsp) will be collected across the two visits (30 ml per day). A typical American Red Cross blood donation is 1 pint (500 ml). Blood may be analyzed for the following: blood lipids and lipoproteins, glucose and insulin, and Fructosamine.

**Central Blood Pressure and Augmentation Index:** Following a 5-minute rest period, brachial artery systolic and diastolic blood pressure will be measured in the left arm using an automated blood pressure cuff. The cuff will reinflate and obtain a pulse wave form. Central blood pressure and wave reflection characteristics (augmentation index) will then be derived from the pressure waveforms using a validated transfer function with a SphygmoCor System (AtCor Medical, Sydney, Australia). This test will be performed in triplicate.

**Pulse Wave Velocity:** Arterial stiffness will be assessed by calculating the pulse wave velocity (PWV) between the carotid and femoral arteries while in the supine position. A cuff will be placed on the participant's thigh. The cuff will inflate during the test to record the pulse waveform in the femoral artery. A simultaneous measurement of the carotid artery pressure waveform will be obtained by an applanation tonometry sensor manually held in place above the carotid artery. PWV will subsequently be calculated by dividing the linear distance between the carotid and femoral sites by the transit time using the SphygmoCor system (AtCor Medical, Sydney Australia). This measurement will be performed in triplicate.

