### 8.2 Sample size determination

If applicable, provide a justification of the sample size outlined in section 8.1 – to include reflections on, or calculations of, the power of the study.

To provide 80% power ( $p<0.05$ ) to detect a minimum 10 mg/dL difference in fasting glucose between the treatments, 45 participants are required (standard deviation of 23.4mg/dL). To account for a 30% drop-out rate, 59 subjects will be randomized. Completion of 45 subjects will also provide 80% power ( $p<0.05$ ) to detect a minimum 11 mg/dL (standard deviation 25.9 mg/dL) difference between the treatment in LDL-cholesterol, and a 4.5 mmHg difference in systolic blood pressure (standard deviation 11 mmHg).

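### Section 8.3 names two comparisons without saying which is primary for fasting glucose; naming one end-of-period contrast, adjusted for period-start glucose already collected, fixes this at almost no cost

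*Combined protocol and SAP*

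**What the plan says.** Section 1.2 gives the primary endpoint as fasting plasma glucose, with no time point or summary measure. Section 8.3, which covers all outcomes, says: "Mixed effect models will be used to determine between-group changes over time and between group differences in mean values following the treatments". The model terms are: "Treatment will be included as a fixed effect. Subject will be included as a random effect". No baseline covariate is listed, and neither comparison is called primary.

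Section 8.2 sizes the trial for 80% power at 10 mg/dL: "difference in fasting glucose between the treatments, 45 participants are required (standard deviation of 23.4mg/dL". It does not say whether that SD belongs to a difference in end values or a difference in changes.

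The start values exist. Section 7.1 says that glucose and the other measures "will be measured at the beginning and the end of each treatment period", and section 7.2.2 adds: "At the beginning and end of each diet period, two fasting blood samples will be collected (separated by at least 24 hours". Section 8.3 does not say how the two draws are combined.

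**The concern.** A change from period start and an end-of-period value are different tests of the same endpoint. They can disagree, and their power differs. With both named and neither ranked, the primary result can be chosen after the data are seen, and the 80% power in section 8.2 is not tied to a defined test.

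There is also an efficiency question. A post-treatment comparison with only treatment and subject in the model ignores the start values. A change score uses them, but only by subtraction, which adds noise when start and end differences are weakly correlated.

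**Working it through.** **Inputs.** From section 8.2: difference 10 mg/dL, SD 23.4 mg/dL, 45 completers, 80% power, p<0.05 (two-sided assumed, because it reproduces the N). From section 7.1: 6-week periods and a wash-out of at least 4 weeks. Not in the documents, so assumed: r, the correlation between a person's peanut-minus-control difference at period start and the same difference at period end; and k, the SD of the start difference divided by the SD of the end difference.

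**1. The plan's own figure.** Paired t-test with 23.4 as the SD of the within-person difference: noncentrality 10/23.4 × √45 = 2.87 on 44 df, power 80.1%. The N of 45 reproduces.

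**2. Either test may count.** With k=1, the two test statistics have correlation √((1−r)/2), which is 0.71, 0.63 and 0.55 at r = 0, 0.2 and 0.4. The chance that at least one is significant at 5% under no effect (bivariate normal) is 8.3%, 8.6% and 8.9%.

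**3. Power if 23.4 is the SD of the end-value difference.**
- End values: SD 23.4.
- Change: SD 23.4 × √(1+k²−2rk). At k=1 this is 33.1, 29.6 and 25.6 for r = 0, 0.2 and 0.4.
- End values adjusted for the start difference: residual SD 23.4 × √(1−r²), 43 df, with the penalty for estimating the slope included. At r=0.4 the residual SD is 21.4.

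| r | End values | Change (k=1) | Adjusted |
|---|---|---|---|
| 0 | 80% | 51% | 79% |
| 0.2 | 80% | 60% | 81% |
| 0.4 | 80% | 73% | 85% to 86% |

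Completers needed for 80% power: end values 45 at every r; change 88, 71 and 54; adjusted 46, 45 and 40. Change-score power also depends on k: at r = 0, 0.2 and 0.4 it is 63%, 72% and 83% for k=0.7, and 40%, 48% and 59% for k=1.3.

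**4. Power if 23.4 is the SD of the difference in changes (k=1).** Change 80% throughout; end values 98%, 94% and 87%; adjusted 97%, 95% and 91%.

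**5. Safety of the adjusted contrast.** Over 24 cases (r = 0, 0.2, 0.4, 0.6; k = 0.7, 1, 1.3; both readings of the SD), its power is at most 1.0 point below the better of the two stated comparisons, and often above it.

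**6. How large can r be?** Draws fall at weeks 0, 6, 10 and 16. If within-person correlation decays as c(t)=exp(−λt), then r = [2c(6) − c(4) − c(16)] / [2(1 − c(10))]. As λ goes to 0 this tends to (−12+4+16)/20 = 0.40. It is 0.27 at λ=0.05 per week and 0.18 at 0.1. With 30% of this variance as visit noise, it reached at most about 0.13 at the rates tried.

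**7. Carryover.** Suppose peanut-first participants start period 2 an assumed 3 mg/dL low and end values are unaffected. With half the participants in that sequence, the mean start difference moves by 1.5, and the adjusted estimate moves by (r/k) × 1.5 in favour of peanut. At r=0.4 that is 0.9, 0.6 and 0.5 mg/dL for k = 0.7, 1 and 1.3.

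**The case against.** The strongest reply is that the documents already lean towards end values. The first hypothesis predicts lower fasting glucose on peanuts than on control, and section 8.2 powers a between-treatment difference whose N reproduces as a paired comparison. This stands as a lean, but neither place ranks the two analyses or defines the SD.

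A reader might try to show an outright conflict by setting the aim's "relationship between markers of glycemic control, after each treatment, and shifts in the microbiota" against the second hypothesis, "Improvements in fasting glucose levels with peanut consumption will be correlated with favorable shifts in the microbiota", and the background's "how changes in the microbiome in response to peanut consumption correlate with changes in glucose regulation". These concern the link between glucose and the microbiota and say little about the primary contrast, so the point does not rest on them.

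A second reply is that naming either stated comparison would cure the ambiguity, and that adjustment is only a preference. This is largely right. Unadjusted end values would be valid. If all of a person's values were equally correlated, as subject being the only listed random effect suggests, r would be 0 and adjustment would lose about 1 point. A reader might infer a gain of about 13 points, which is what r=0.6 would give. The documents supply no r, and the visit schedule does not support one that high under the decay model above. A longer wash-out or a person-by-period effect could raise r, but the documents support neither.

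Two other strong readings fail. The N of 45 is not wrong. Nor is period-start glucose unused: the change comparison needs it as part of the response. What is missing is its use as a covariate.

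**Conclusion.** The point holds as a cheap improvement. The primary test of fasting glucose is not fixed in advance. The consequences are a type I error of about 8% to 9% if either comparison may count (equal SDs), and change-score power of 51% to 73% for r from 0 to 0.4 if 23.4 is the SD of the end-value difference and the SDs are equal. The first figure applies only if both tests are allowed to count; the second depends on an r and k that the documents do not give.

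The main benefit of the adjusted contrast is a single pre-named test that needs no guess about r: over the cases computed it is within about 1 point of the better stated comparison, or above it. Its gain over unadjusted end values is about −1 to +5 points for r from 0 to 0.4. The need to name one contrast does not depend on r.

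**What to change.** In section 8.3, name one primary contrast: peanut minus control in end-of-period fasting glucose (mean of the two end draws), two-sided 5%, from the planned mixed model with treatment fixed and subject random. Add period-start glucose as two covariates: the participant's mean of the start values (each the mean of its two draws) over the periods that have an end value, and the period-specific deviation from that mean. For completers this equals adjusting for the within-person start difference. A participant with one period stays in with deviation zero, which fits the allowance in section 3.3.2 for using withdrawn participants' data. Report unadjusted end values and change from start as supportive. In section 8.2, state which quantity the 23.4 mg/dL SD describes.

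The cost is wording and one or two degrees of freedom (about 1 point of power if r=0), with no new visits or samples. The real downside is carryover: an assumed 3 mg/dL residual in the period-2 start value would shift the adjusted estimate by about 0.5 to 0.9 mg/dL towards peanut at r=0.4. The unadjusted supportive analysis is free of this shift, but it cannot diagnose it, because the two estimates differ by chance with a standard error of about 1.5 mg/dL at r=0.4 (k=1).

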## 8.0 Subject Numbers and Statistical Plan

### 8.1 Number of Subjects

Indicate the total number of subjects to be accrued.

If applicable, distinguish between the number of subjects who are expected to be enrolled and screened, and the number of subjects needed to complete the research procedures (i.e., numbers of subjects excluding screen failures.)

Approximately 135 subjects will complete the screening process for this study; of those we anticipate 59 subjects to be eligible A total of 45 participants will complete the study. To achieve this, we will likely need to randomize 59 subjects assuming a 30% drop out rate.

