#### **9.1.4 Transferring Data and/or Specimens**

If the data and/or specimens will be transferred to and/or from outside collaborators, identify the collaborator to whom the data and/or specimens will be transferred and how the data and/or specimens will be transferred. This information should not conflict with information provided in section 9.1.1.1 regarding who has access to identifiable information, if applicable.

After collection, serum and plasma are transferred to ~1 mL aliquots – these vials contain only the participants study ID #, sample type (serum or plasma) and time point. The vials are then boxed and stored in a locked -80 degree freezer until all data collection is complete. Fecal samples will also be stored in a locked -80 degree freezer and the vials will contain no identifying information. Once the study is complete the samples will be sorted and

shipped on dry ice via FedEx or a Quest Courier to the following sites for analysis: (No identifying information is provided with the samples)

Serum/Plasma:

- Quest diagnostics, [name]

Fecal samples:

- Wright Labs LLC, [name]

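### The crossover model names treatment and subject but not period; adding period is a cheap, optional gain in precision

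*Combined protocol and SAP*

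**What the plan says.** Section 7.1 sets the design: "A two-period randomized crossover trial will be conducted". Each treatment lasts six weeks, with a washout of at least four weeks between them. Fasting glucose and the other outcomes "will be measured at the beginning and the end of each treatment period".

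Section 8.3 says mixed models will be used for "between-group changes over time and between group differences in mean values following the treatments". It then lists the terms: "Treatment will be included as a fixed effect. Subject will be included as a random effect". Neither that section nor any other names a period or sequence term. The reference to change over time concerns change across visits and does not put period into the model.

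Section 8.2 bases the size on glucose: "45 participants are required (standard deviation of 23.4mg/dL", for a 10 mg/dL difference at 80% power. Section 8.1 agrees on the number of completers: "A total of 45 participants will complete the study". The documents do not state how participants are allocated to the two orders.

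**The concern.** In a two-period crossover, a general shift in glucose between periods enters each participant's peanut-minus-control difference with one sign in one order and the opposite sign in the other. A model with a period term removes it. A model with only treatment and subject leaves it in, with two effects on the comparison of post-treatment means:

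- The shift inflates the residual variance, so the standard error is larger than it needs to be.
- For a given unequal split of completers between orders, the estimate moves by shift × (difference in order sizes)/N. This is chance imbalance. Over the randomisation, with dropout unrelated to order, it averages to zero.

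Unequal splits are plausible. Section 8.2 expects 30% dropout, and section 3.3.2 replaces people who withdraw without saying which order the replacement receives. What is at stake is some power for the primary endpoint.

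**Working it through.** **Inputs.** Target 10 mg/dL, SD 23.4 mg/dL, 80% power and p<0.05 (section 8.2); 45 completers of 59 randomised (sections 8.1 and 8.2). Assumed: a two-sided test, 23.4 as the SD of the within-person difference, and period shifts of 0, 5 and 10 mg/dL.

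**1. Reproduce the plan's figure.** Paired t-test on within-person differences: SE = 23.4/√45 = 3.49, noncentrality 10/3.49 = 2.87, 44 df. Power is 80.06%, and 45 is the smallest N that reaches 80%. The plan's N therefore matches a paired analysis with no period effect.

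**2. Set up the two analyses.** Let π be the shift from period 1 to period 2, with n1 completers taking peanuts first and n2 taking control first. The expected difference is τ − π in the first group and τ + π in the second.

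- *Without period:* the mean of all differences has expectation τ + π(n2 − n1)/N. The sum of squares is noncentral chi-square with noncentrality 4·n1·n2·π²/(N·SD²). Power follows by numerical integration, with N − 1 df.
- *With period:* the estimate is the average of the two group means, SE = (SD/2)·√(1/n1 + 1/n2), with N − 2 df. Power does not depend on π.

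**3. Average over chance splits of the 45 completers.** The split is hypergeometric if 59 are allocated 30/29 and losses are random, and binomial under simple randomisation.

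| Shift (mg/dL) | 30/29: without / with period | Simple: without / with period |
|---|---|---|
| 0 | 80.06% / 79.8% | 80.06% / 79.1% |
| 5 | 78.6% / 79.8% | 78.3% / 79.1% |
| 10 | 74.3% / 79.8% | 73.2% / 79.1% |

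The period term raises average power once the shift exceeds about 2.2 mg/dL (30/29) or 3.7 mg/dL (simple).

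**4. Particular splits.** Ranges show the two directions of the shift.

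| Split | Shift 5, without | Shift 10, without | With period |
|---|---|---|---|
| 22/23 | 77.8–79.6% | 72.7–76.7% | 80.0% |
| 20/25 | 74.0–83.0% | 64.0–83.6% | 79.5% |

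At 20/25 the estimate is displaced by 5 × 5/45 = 0.6 mg/dL or 10 × 5/45 = 1.1 mg/dL. A difference of five or more between orders has probability 23% (30/29) or 55% (simple).

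**5. Type I error without period.** Averaged over splits it is 4.6% (shift 5) and 3.7% (shift 10) under 30/29, and 5.0% under simple randomisation, so the test is valid or conservative. Given one very lopsided split it can exceed 5%: at 28/17 with a 10 mg/dL shift, simulation gives 7.8%.

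**6. Completer equivalents.** Using variance SD² + shift², the SD becomes √(547.56 + 25) = 23.9 or √(547.56 + 100) = 25.4. About 47 or 53 completers would then be needed for 80% power without period. This holds only if 23.4 excludes the shift.

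**The case against.** The strongest reply is that section 8.3 is a few sentences in an ethics-board template. Treatment and subject alone cannot even model change over time, so the list may be shorthand and period may be intended. That is possible. Nothing in the text supplies the term, though, and an analyst following it literally would leave it out.

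Several limits stand:

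- **No shift is documented.** The documents give neither a size nor a cause. Assay drift is unlikely because samples are "stored in a locked -80 degree freezer until all data collection is complete". Recruitment is spread over time (section 4.2), so seasonal effects need not form one common shift. A 10 mg/dL shift equals the whole target effect and is large against the entry range of 100 to 126 mg/dL. At 5 mg/dL the gain is about one point of power.
- **The change analysis is largely protected.** A level shift already present at the period-2 baseline cancels from within-period change. The figures above apply to post-treatment means, which section 8.3 also plans to compare.
- **The SD's origin is not stated.** If 23.4 already contains a period shift, planned power is kept without the term: about 80.5% (shift 5) and 82.2% (shift 10) at 22/23. Period would still raise it to about 81.8% and 87.3%.
- **The calculation is simplified.** It uses completers and a paired t-test, not the planned mixed model with possible data from withdrawals. The powers are a guide, and the decimals should not be over-read.

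None of this removes the point; it keeps it small.

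**Conclusion.** The concern holds as an optional improvement. The stated model has no period term, and a model with one is better whenever glucose shifts by more than about 2 to 4 mg/dL between periods. On average over completer splits, the gain is about 1 point of power at an assumed 5 mg/dL shift and between 5 and 6 points at 10 mg/dL. With no shift, nothing is lost by the present model.

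The sample size of 45 is not shown to be wrong, and the treatment estimate is not biased over the randomisation. These conclusions rest on the assumed shifts, on dropout unrelated to order, and on reading 23.4 mg/dL as the SD of within-person differences, which is the reading that reproduces 45.

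**What to change.** Amend section 8.3 so that the mixed model has treatment and period as fixed effects and subject as a random effect. If period was always intended, the sentence simply records it and removes a choice that could otherwise be made after the data are seen.

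The cost is one degree of freedom and a variance inflation of N²/(4·n1·n2): 2025/2024 = 1.0005 at 22/23 and 2025/2000 = 1.0125 at 20/25. If there is no shift, power goes from 80.06% to 80.00% at 22/23 and to 79.5% at 20/25. Averaged over splits, it goes to 79.8% under 30/29 or 79.1% under simple randomisation. No extra participants, visits or measurements are needed.
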